- Major protocol violation (patient lost to follow-up, hospitalization resulting from major side effects, lack of consent, lack of safety laboratory tests)
- Lost to follow-up (We will make every effort to follow all randomized patients including contact of family members and/or other medical facilities to avoid losing patients to study follow-up)
- Death
- For patients who experience an adverse event requiring cessation of study drug, they will be followed until the event resolves, until they begin another clinical trial, or until the end of the study. However, certain adverse events (e.g., a cerebrovascular accident, worsening hypertension) will not be expected to resolve completely; in these cases, the date and time should be recorded when the event reaches its new, stable equilibrium and any remaining residual of the event should be documented.
- Suspected pregnancy
- We will add replacement patients to account for withdrawals until we reach 30 total patients.

Classifications for adverse event assessment

All AEs will be assessed and documented by the investigator according to the categories detailed below.

Seriousness

For each AE, the seriousness must be determined according to the criteria given in Section F below

• Intensity

The intensity of the AE is classified according to the CTCAEv4.0. Grade refers to the severity (intensity) of the AE:

- **CTCAEv4 Grade 1**: mild; asymptomatic or mild symptoms; clinical or diagnostic observations only; intervention is not indicated.
- **CTCAEv4 Grade 2**: moderate; minimal, local, or noninvasive intervention is indicated; limiting to age-appropriate instrumental activities of daily living (ADL; instrumental ADL refers to preparing meals, shopping for groceries or clothes, using the telephone, managing money, etc).
- **CTCAEv4 Grade 3**: Severe or medically significant but not immediately life threatening; hospitalization or prolongation of hospitalization is indicated; disabling; limiting to self care ADL (self care ADL refers to bathing, dressing and undressing, feeding self, using the toilet, taking medications, and not bedridden).

CTCAEv4 Grade 4: life-threatening consequences; urgent intervention is indicated.

CTCAEv4 Grade 5: death due to an AE.

Expected adverse events such as headache, fatigue, nausea, diarrhea, and AEs assessed as Grades 1 and 2 will not require reporting to Helsinn. Adverse events will be tracked and submitted during annual review to the IRB. Adverse events (including event name, grade, start/stop date and attribution) will be entered into Prometheus. The Principal Investigator or physician designee will verify the attribution assigned in Prometheus by signing the Prometheus adverse events printout at the end of protocol treatment. Prometheus will be utilized as the electronic case report form for this study.

Causal relationship

The assessment of the causal relationship between an AE and the administration of treatment is a clinical decision based on all available information.

The causality assessment should be done separately for each study treatment.

The assessment is based on the question whether there was a "reasonable causal relationship" to the study treatment in question.

Possible answers are "yes" or "no". An assessment of "no" would include:

1. The existence of a clear alternative explanation, e.g. mechanical bleeding at surgical site.

or

2. Non-plausibility, e.g. the subject is struck by an automobile when there is no indication that the drug caused disorientation that may have caused the event; cancer developing a few days after the first drug administration.

An assessment of "yes" indicates that there is a reasonable suspicion that the AE is associated with the use of the study treatment.

Factors to be considered in assessing the relationship of the AE to study treatment include:

- The temporal sequence from drug administration: The event should occur after the drug is given. The length of time from drug exposure to event should be evaluated in the clinical context of the event.
- Underlying, concomitant, intercurrent diseases: Each event should be evaluated in the context of the natural history and course of the disease being treated and any other disease the subject may have.
- Concomitant medication or treatment: The other drugs the subject is taking or the treatment the subject receives should be examined to determine whether any of them may be suspected to cause the event in question.
- The pharmacology and pharmacokinetics of the study treatment: The pharmacokinetic properties (absorption, distribution, metabolism and excretion) of the study treatment, coupled with the individual subject's pharmacodynamics should be considered.

F. Investigator Communications with Helsinn

As stipulated in 2.6 of the Strategic [name] Anderson is the sponsor and assumes all obligations regarding the preparation and submission of individual and aggregate safety reports to FDA, Ethic Committee, and other relevant persons to the extent required by and as per the applicable US laws, regulations, and guidelines. The Principal Investigator will forward to Helsinn any serious adverse reaction (i.e. for which it is judged there is a reasonable causal relationship between the study drug and the adverse event) on the MedWatch Form, regardless of its expectedness, within 24 hours from first awareness, including follow-ups.

The Principal Investigator shall provide Helsinn with relevant safety data including study and IND safety reports (prior to their finalization) and any safety signal or risk (with the rationale) originating from the study. The e-mail address for exchanging all the above mentioned safety information is: [contact].

Attribution	Grade 1	Grade 2	Grade 3	Grade 4	Grade 5
Unrelated	Phase I	Phase I	Phase I	Phase I	Phase I
			Phase II	Phase II	Phase II
				Phase III	Phase III
Unlikely	Phase I	Phase I	Phase I	Phase I	Phase I
-			Phase II	Phase II	Phase II
				Phase III	Phase III
Possible	Phase I	Phase I	Phase I	Phase I	Phase I
	Phase II	Phase II	Phase II	Phase II	Phase II
		Phase III	Phase III	Phase III	Phase III
Probable	Phase I	Phase I	Phase I	Phase I	Phase I

Recommended Adverse Event Recording Guidelines

					Page 17 of 22
	Phase II	Phase II	Phase II	Phase II	Phase II
		Phase III	Phase III	Phase III	Phase III
Definitive	Phase I	Phase I	Phase I	Phase I	Phase I
	Phase II	Phase II	Phase II	Phase II	Phase II
		Phase III	Phase III	Phase III	Phase III

Adverse events will be captured according to the recommended AE recording guidelines for a Phase II protocol.

G. Serious Adverse Event Reporting

An adverse event or suspected adverse reaction is considered "serious" if, in the view of either the investigator or the sponsor, it results in any of the following outcomes:

- Death
- A life-threatening adverse drug experience any adverse experience that places the
 patient, in the view of the initial reporter, at immediate risk of death from the adverse
 experience as it occurred. It does not include an adverse experience that, had it
 occurred in a more severe form, might have caused death.
- Inpatient hospitalization or prolongation of existing hospitalization
- A persistent or significant incapacity or substantial disruption of the ability to conduct normal life functions.
- A congenital anomaly/birth defect.

Important medical events that may not result in death, be life-threatening, or require hospitalization may be considered a serious adverse drug experience when, based upon appropriate medical judgment, they may jeopardize the patient or subject and may require medical or surgical intervention to prevent one of the outcomes listed in this definition. Examples of such medical events include allergic bronchospasm requiring intensive treatment in an emergency room or at home, blood dyscrasias or convulsions that do not result in inpatient hospitalization, or the development of drug dependency or drug abuse (21 CFR 312.32).

- Important medical events as defined above, may also be considered serious adverse events. Any important medical event can and should be reported as an SAE if deemed appropriate by the Principal Investigator or the IND Sponsor, IND Office.
- All events occurring during the conduct of a protocol and meeting the definition of a SAE must be reported to the IRB in accordance with the timeframes and procedures outlined in "The University of Texas M. D. Anderson Cancer Center Institutional Review Board Policy for Investigators on Reporting Serious Unanticipated Adverse Events for Drugs and Devices". Unless stated otherwise in the protocol, all SAEs, expected or unexpected, must be reported to the IND Office, regardless of attribution (within 5 working days of knowledge of the event).
- All life-threatening or fatal events, that are unexpected, and related to the study drug, must have a written report submitted within **24 hours** (next working day) of knowledge of the event to the Safety Project Manager in the IND Office.
- Unless otherwise noted, the electronic SAE application (eSAE) will be utilized for safety reporting to the IND Office and MDACC IRB.

- Serious adverse events will be captured from the time of the first protocol-specific intervention, until 30 days after the last dose of drug, unless the participant withdraws consent. Serious adverse events must be followed until clinical recovery is complete and laboratory tests have returned to baseline, progression of the event has stabilized, or there has been acceptable resolution of the event.
- Additionally, any serious adverse events that occur after the 30 day time period that are related to the study treatment must be reported to the IND Office. This may include the development of a secondary malignancy.

Reporting to FDA:

• Serious adverse events will be forwarded to FDA by the IND Sponsor (Safety Project Manager IND Office) according to 21 CFR 312.32.

It is the responsibility of the PI and the research team to ensure serious adverse events are reported according to the Code of Federal Regulations, Good Clinical Practices, the protocol guidelines, the sponsor's guidelines, and Institutional Review Board policy.

H. Statistical Considerations

The primary objective of this phase II study is to estimate the effect of NEPA on the nausea numeric rating scale (i.e. change between day 5 and day 15). The target accrual is 30 evaluable patients who complete the study with a randomization ratio of 2:1 (NEPA vs Placebo), but accrual will range from 41-50, given an attrition rate of 30-40%. With 20 patients in the NEPA arm, we would have a 92% power to detect a difference of 2 points with a standard deviation of 2.5 (effect size of 0.8) using two-sided paired t-test with a significance level of 0.05.

Descriptive statistics, including mean, standard deviation, 95% confidence intervals, median, range, frequency and percentage will be summarized for all variables of interest such as patients' demographics, clinical characteristics, personalized nausea goal, NRS and adverse effects, whichever appropriate.

We will focus on estimating the magnitude of change in NRS between day 5 and day 15. We will use a mixed model to examine the change in nausea overtime in both the NEPA arm and placebo arm.

We will estimate the proportion (with 95% confidence interval) of patients who achieve their personalized nausea goal for NEPA and placebo as a secondary outcome. Adverse effects associated with NEPA and placebo will be collected and frequency will be summarized.

A comparison between NEPA and placebo is not the objective of this study. However, Chi-squared test or Fisher's exact test, whichever the most appropriate, will be used to test for association between categorical variables, such as CTCAE adverse effects, global assessment, and blinding. Wilcoxon rank sum test or Kruskal-Wallis test will be used to test for difference of continuous variables, such as ESAS and FLIE. General linear model may be considered to examine the effect of potential important factors on NRS.

A Response/Toxicity Summary will be submitted to the IND Office Medical Monitor, after the first ten evaluable patients complete study treatment, and every 10 evaluable patients thereafter.

I. Data Confidentiality Procedures

This study will be monitored by the MD Anderson IND Office and a protocol-specific monitoring plan will be followed.

All records identifying the subject will be kept confidential and, to the extent permitted by the applicable laws and/or regulations, will not be made publicly available.

During the study, trained research staff will be performing study assessments and monitoring the patient carefully throughout the study period. Regulatory monitoring will be provided by the principal investigator and the IND office. Patient confidentiality will be maintained by use of unique study numbers, secure storage of clinical data, and anonymous reporting.

Collection of identifiers: We will collect and securely store patients' identifiers (including name and medical record number). Each patient will be assigned a study number that will be the only identifier to figure in the analytical file and personal data will not be disclosed in any form. The key linking these numbers will be retained in a securely locked file by the investigator.

Data Storage: Protection of electronic and paper records will be maintained to the best of our ability. All electronic records will be stored on password-protected institution computers behind the institution firewall. Any paper records will be classified and stored in locked files inside a locked office.

Training of personnel: Only MDACC personnel trained in maintaining confidentiality, the principal investigators, co-investigators, and the research team will have access to study records.

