IND Agent: NEPA (300mg Netupitant/0.5mg Palonosetron) Capsule (Refer to Investigator's Brochure for further information)

Chemical Name: 2-[3,5-Bis(trifluoromethyl)phenyl]-N-[6-(4-methylpiperazin-1-yl)-4-o-tolylpyridin-3-yl]-N-methylisobutyramide

Mode of Action: NEPA is a fixed combination of netupitant, a substance P/neurokinin 1 (NK) receptor antagonist, and palonosetron, a serotonin-3 (5-HT) receptor antagonist

Description: NEPA (300mg netupitant/0.5mg palonosetron) capsules are hard gelatin capsules with white body and caramel cap with "HE1" printed on the body. Placebo for NEPA will be identical hard gelatin capsules with the "HE1" imprinted on the body.

How Supplied: Helsinn will supply NEPA and Placebo capsules to the site. The capsules are packaged as 1 capsule per blister pack/box.

Note: NEPA/Placebo may be repackaged from the supplied bottles and dispensed in pharmacy dispensing bottles according to the quantities specified by the investigator.

Storage: The recommended long term storage condition for NEPA/placebo capsules is USP controlled room temperature. Store at 20-25 °C (68-77 °F). Excursions permitted to 15-30 °C (59-86 °F).

Stability: NEPA/Placebo has a shelf-life of 4 years from date of manufacture.

Route(s) of Administration: Oral

Method of Administration: It is recommended patients should take NEPA (300mg netupitant/0.5mg palonosetron)/Placebo (1 capsule) orally with or without food.

Please refer to the NEPA package insert for safety profile and side effects/drug interactions.

Potential Drug Interactions: CYP3A4 Interactions:

 Akynzeo should be used with caution in patients receiving concomitant medications that are primarily metabolized through CYP3A4. The plasma concentrations of CYP3A4 substrates can increase when co-administered with Akynzeo. The inhibitory effect on CYP3A4 can last for multiple days. Patients on these medications will be monitored while on study.

Concomitant and Prohibited Medication

- Concomitant medications must be recorded in the electronic medical record from 28 days prior to the first dose of study drug through the last dose of study drug.
- The use of rescue medications will be allowed (metoclopramide 10 mg q4h PRN for breakthrough nausea).

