- As specified within the Exclusion Criteria, scheduled strong or moderate CYP 3A4 inhibitors (boceprevir, clarithromycin, conivaptan, indinavir, itraconazole, ketoconazole, lopinavir/ritonavir, mibefradil, nefazodone, nelfinavir, posaconazole, ritonavir, saquinavir, telaprevir, telithromycin, voriconazole; amprenavir, aprepitant, atazanavir, ciprofloxacin, darunavir/ritonavir, diltiazem, erythromycin, fluconazole, fosamprenavir, grapefruit juice, imatinib, verapamil) are prohibited within one week of study enrollment. If a patient is required to take a strong CYP3A4 inhibitor while enrolled in this trial, they must be discontinued.
- As specified in the Exclusion Criteria, the administration of scheduled CYP3A4 substrates with narrow safety range at the time of study enrollment (alfentanil, cyclosporine, dihydroergotamine, ergotamine, pimozide, quinidine, sirolimus, tacrolimus) are prohibited. If a patient is required to take any of these drugs while enrolled in this trial, they must first be discontinued.

Drug Accountability:

Agent Ordering:

[figure not shown]
Helsinn will ship the medication to the Investigational Pharmacy Services. Drug reordering will be via a drug order form or electronic/fax communication with the Helsinn representatives. **Agent Inventory Records** – The investigator, or a responsible party designated by the investigator, will maintain a record of the inventory and disposition of all agents received from Helsinn. Sites may use their own drug accountability logs per their standard procedures. Drug Accountability records will capture Lot numbers dispensed to the patient. Unused drug at the remainder of the trial and expired drug may be destroyed on site per the site's drug expiration policy or Helsinn will make arrangements for destruction.

Dose: Dose will be 300mg netupitant/0.5mg palonosetron. NEPA (300mg netupitant/0.5mg palonosetron)/Placebo capsules will be used in this study. No other capsule strengths are available and there are no permitted dose reduction schemes. Dosing may be delayed/interrupted at the discretion of the Investigator if needed due to an adverse event, and discussed with the patient.

D. Experimental Approach

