- 2. Clinical evidence of bowel obstruction at the time of study enrollment
- 3. Expected to use other 5HT3 antagonists or NK1 antagonists for prophylaxis during the study
- 4. Continuation of over-the-counter therapies for nausea and/or vomiting during the study
- 5. On cytotoxic chemotherapy in the high/moderate/low emetogenic risk categories or oral antineoplastic agents in the high or moderate emetogenic risk categories according to the latest NCCN guideline within 2 weeks of study enrollment
- 6. On scheduled potent CYP3A4 inducers at the time of study enrollment (avasimibe, carbamazepine, phenytoin, rifampin, efavirenz, nevirapine, barbiturates, systemic glucocorticoids, modafinil, oxcarbazine, phenobarbital, pioglitazone, rifabutin, St. John's wort, troglitazone)¹
- 7. On scheduled CYP3A4 substrates with narrow safety range at the time of study enrollment (alfentanil, cyclosporine, dihydroergotamine, ergotamine, pimozide, quinidine, sirolimus, tacrolimus)
- 8. On scheduled strong or moderate CYP3A4 inhibitors (boceprevir, clarithromycin, conivaptan, indinavir, itraconazole, ketoconazole, lopinavir/ritonavir, mibefradil, nefazodone, nelfinavir, posaconazole, ritonavir, saquinavir, telaprevir, telithromycin, voriconazole; amprenavir, aprepitant, atazanavir, ciprofloxacin, darunavir/ritonavir, diltiazem, erythromycin, fluconazole, fosamprenavir, grapefruit juice, imatinib, verapamil) within one week of study enrollment¹
- 9. Unwilling to provide informed consent
- 10. Severe renal impairment (calculated Creatinine clearance <=29 cc/min)²
- 11. Severe liver impairment (Child-Pugh Score >9)³
- 12. Females who are pregnant, lactating, or intend to become pregnant during the participation of the study; childbearing age women who are not on birth control. Positive pregnancy test for women of childbearing potential, as defined by intact uterus and ovaries, and no history of menses within the last 12 months. Pregnancy test to be performed on the day of enrollment. In cases of women with elevated b-HCG, these candidates will be eligible to participate so long as the level of b-HCG is not consistent with pregnancy and the non-pregnant status is confirmed by a Gynecologic examination.

¹ according to FDA website

http://www.fda.gov/Drugs/DevelopmentApprovalProcess/DevelopmentResources/DrugInteractionsLabelin g/ucm093664.htm

² Calculated creatinine clearance can be done within 14 days of study enrollment.

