* Assessments may be done over the phone or in person from day 1 to day 15±2, and on day 20±2 and 25±2. For the other days starting day 16 (open label phase), patients will continue to complete assessments in the diary on their own until the end of study.

¹ Optional extension phase

² patient initials, medical record number, date of birth, sex, race, education, marital status, cancer diagnosis, stage, co-morbidities, cause(s) of nausea, date of last cancer treatment, Karnofsky Performance status, Memorial Delirium Assessment Scale (MDAS).⁴¹

³ all scheduled and as needed medications that could be used to treat nausea, such as metoclopramide, haloperidol, olanzapine, corticosteroids, 5HT3 antagonists, antihistamines, anticholinergics will be documented.

⁴ To evaluate the efficacy of NEPA/placebo, each patient will complete a diary from time of enrollment through the end of study documenting the average intensity of nausea over the preceding 24 h using a 0-10 NRS (where 0=no nausea and 10=worst possible), the worst intensity of nausea over the preceding 24 h using the same 0-10 NRS (where 0=no nausea and 10=worst possible), the number of doses of rescue antiemetic (i.e. metoclopramide) and total dose over the past 24 hours, and the Index of nausea and vomiting and retching (see Section D.10).

⁵ validated questionnaire that measures 9 other common symptoms in the past 24 hours (pain, fatigue, nausea, depression, anxiety, drowsiness, shortness of breath, appetite, sleep, and feeling of well-being) using numeric rating scales.⁴²

⁶ we will assess personalized nausea goal by asking "At what level of intensity would you feel comfortable? 0-10 where 0=no nausea and 10=worst possible" ⁴⁰. Personalized nausea response is defined as nausea NRS \leq personalized nausea goal. To assess stability of personalized nausea goal, we will be asking participants to provide this on day 15±2 as well.

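### Exclusion 7 lets in patients with as-needed or expected use of narrow-safety-range CYP3A4 substrates; stopping first leaves residual netupitant, and concomitant-medication recording ends at the last dose

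*Combined protocol and SAP*

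**What the plan says.** Table 2 in Section D.2, exclusion 7, applies to patients "On scheduled CYP3A4 substrates with narrow safety range at the time of study enrollment" and lists eight drugs. Section C, under Concomitant and Prohibited Medication, repeats the bar with the same limits: "the administration of scheduled CYP3A4 substrates with narrow safety range at the time of study enrollment". If the need arises later, the rule is "If a patient is required to take any of these drugs while enrolled in this trial, they must first be discontinued". No interval after the last NEPA capsule is given.

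On the interaction itself, Section C states: "Akynzeo should be used with caution in patients receiving concomitant medications that are primarily metabolized through CYP3A4". It adds: "The inhibitory effect on CYP3A4 can last for multiple days. Patients on these medications will be monitored while on study". For further detail it says: "Please refer to the NEPA package insert for safety profile and side effects/drug interactions".

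Section B.4 gives netupitant a half-life of 80 ± 29 h. Section D.7 puts the capsules on days 6 and 11 (blinded) and days 16 and 21 (open label). Under Section C, concomitant medications are recorded from 28 days before the first dose up to the last dose. Under Section G, SAEs are captured until 30 days after the last dose.

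**The concern.** The plan lists these eight drugs because NEPA can raise the levels of CYP3A4 substrates and these have little margin. That reason does not depend on whether a dose is scheduled or taken as needed, but the entry criterion does. A patient holding a listed drug for as-needed use, or expected to need one during the study, meets the criteria and can be given an active capsule.

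If the drug is then needed, the patient leaves study treatment, but the netupitant already taken does not leave with that decision. Nothing in the protocol text says what the treating team should be told at that moment. Once the last capsule has been taken, nothing requires the substrate's use to be recorded. At stake is the safety of an occasional patient and the ability to interpret an event if one occurs.

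**Working it through.** **Text check**

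1. Does the word scheduled exclude as-needed use? Table 4, footnote 3 collects "all scheduled and as needed medications that could be used to treat nausea", so the protocol treats the two as separate categories. Exclusion 7 names only one of them, and no other criterion covers as-needed use of these eight drugs.
2. Could the plan have looked ahead? Exclusion 3 does so: "Expected to use other 5HT3 antagonists or NK1 antagonists for prophylaxis during the study". Exclusion 7 looks only at enrolment.
3. What does the on-study clause achieve? It covers any of the listed drugs, scheduled or not. Its pronoun is ambiguous. If it means the patient, as in the preceding bullet on inhibitors, the substrate may start straight after discontinuation. If it means the drugs, it contradicts the premise that they are required. Neither reading separates the substrate from NEPA.
4. When does recording stop? At the last dose: day 11, or day 21 with the extension. The diary continues, but Section D.8 and Table 4 direct it to antiemetic and rescue use.

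**Residual netupitant**

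The plan gives no figure on this, so there is none to reproduce. Input: half-life h = 80 h, with 51 and 109 h from 80 − 29 and 80 + 29 (a bracket, not a full range). Assumptions: first-order decay, absorption time ignored, and repeat capsules 5 days apart added together.

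Fraction of one capsule left after t hours = 2^(−t/h). At 5 days (t = 120), call this r. Relative to the starting level from one capsule, the amount left 5 days after the last capsule is r after one, r + r² after two, and r + r² + r³ + r⁴ after four. At 30 days (t = 720), the one-capsule fraction is 2^(−720/h). For four capsules it is multiplied by P = 1 + r + r² + r³.

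| | h = 51 | h = 80 | h = 109 |
|---|---|---|---|
| 5 days, one capsule | 0.196 | 0.354 | 0.466 |
| 5 days after the second of two | 0.234 | 0.479 | 0.684 |
| 5 days after the fourth of four | 0.243 | 0.538 | 0.832 |
| P, just after the fourth | 1.242 | 1.523 | 1.785 |
| 30 days, one capsule | 0.0001 | 0.0020 | 0.0103 |
| 30 days after the fourth | 0.0001 | 0.0030 | 0.0183 |

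For example, at h = 80 h, 2^(−120/80) = 2^(−1.5) = 0.354, or 35%.

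Exposure is therefore substantial 5 days after stopping and is near its highest when recording ends. By 30 days it is 0.2% (0.01–1.0%) after one capsule and 0.3% (0.01–1.8%) after four, so the existing SAE window is long enough for the record proposed below.

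These figures do not apply during the placebo run-in, or to patients randomized to placebo unless they enter the open-label extension.

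**The case against.** The strongest reply is that the gap is narrow and already guarded. The on-study clause reaches as-needed use as soon as a listed drug is required. Concomitant medication is recorded from 28 days before dosing, so recent as-needed use should be visible. Section C adds a caution, monitoring while on study, and a reference to the package insert, which may already give specific advice. Section E has other drugs examined when an event is assessed for causality, and Section D.5 allows unblinding for a safety issue when the treating physician needs the assignment. The limit to scheduled use also runs through exclusions 6, 7 and 8, so it looks like a deliberate choice. Exclusion 3 is only a loose comparison, since it concerns drugs of the same classes as NEPA. The documents name no listed drug that an eligible outpatient would take as needed.

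Most of this stands, and it limits the weight of the point. It does not close the gap. Recording as-needed use does not exclude it. The monitoring has no stated method or end, and does not clearly reach a patient just discontinued. Causality review acts only after an event.

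Three stronger readings are tempting and should not be drawn:

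- **That patients are unprotected.** The safeguards above show otherwise, and the package insert and Investigator's Brochure are not available here.
- **That the decay figures give a required washout**, such as five half-lives (5 × 80 / 24 = 16.7 days). That rule is not in the documents, which give no relation between exposure and inhibition.
- **That the substrate should be withheld, or that unblinding is never needed.** With 2:1 randomization, about one third of blinded patients have had no NEPA and carry no interaction risk. Delaying a required drug could harm them, and the Section D.5 route exists for such a case.

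**Conclusion.** The point holds as a low-priority safety gap in the protocol text. The entry rule admits as-needed and expected users, discontinuation alone does not remove netupitant, and the substrate record stops when exposure is high. Its size in exposure terms is about 35% (20–47%) of one capsule left at 5 days, and more after repeat capsules; this is not a measure of inhibition.

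The number of patients affected should be small: 20 evaluable NEPA patients are planned, within an accrual of 41–50, and the documents give no frequency of use. The sample size, the 92% power statement in Section H and the efficacy estimates are untouched. The conclusion rests on the protocol's own distinction between scheduled and as-needed use, and on the assumption that the package insert does not already settle the matter.

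**What to change.** (a) Reword exclusion 7, and the matching sentence in Section C, to: *Current use (scheduled or as needed), or expected use during the study, of CYP3A4 substrates with narrow safety range*, followed by the same eight drugs.

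(b) Add to Section C that use of these substrates is recorded until 30 days after the last capsule, blinded or open label, within the existing SAE follow-up. When a patient is discontinued because one is needed, tell the treating team that NEPA exposure is possible and that CYP3A4 inhibition may persist for several days. Follow the package insert for any interval, and use the Section D.5 unblinding route if the treating physician needs the assignment. Do not write in a fixed number of half-lives or an instruction to delay the substrate.

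Cost: a few as-needed users become ineligible, and one follow-up question is added.
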